## 12.0 Confidentiality

**12.1 Data Storage.** All information collected for research purposes will be de-identified. Identifying information (names, addresses and phone numbers) will be used initially only to identify potential patients to approach. The only link between the participant identifiers and their study identifier will be kept on a password protected database and in a locked filing cabinet. There are no patient identifiers collected and retained for research purposes. Feasibility data will represent only frequencies and percentages.

**12.2 Patient Identifiers within stored data.** No participant identifiers will be kept with or included in the study data. All identifying patient information will be stored on a secure database, or in a locked filing cabinet with the study team. This data will be stored and maintained for a minimum of ten years or until final analyses are completed, whichever occurs last, in order to ensure data quality.

**12.3 Study-wide data management.** Individual sites will be responsible for original source data (surveys, Case Report Forms) until study completion. All such materials will be stored in a locked file cabinet or other office with access only to study staff. Upon study completion (last data collection for last patient), all materials will be de-identified (labeled only with study ID) and faxed or scanned to the coordinating center for electronic storage. As described above, monthly site data collection responsibilities will include monitoring of local data completeness and troubleshooting with the coordinating center for data completion, if necessary. Per the Data Transfer Agreement, a Limited Data Set will be transmitted by Seattle Children's research staff to external collaborators using a secure, institutionally approved method. Any data provided from SCH to [name] and DFCI for oversight purposes during active data completion will also be limited.

When Zoom is used, the following actions will be taken to protect confidentiality and privacy:

1. The latest version of Zoom that is available will be used.
2. The meeting room will be set to private.
3. A password/passcode will be required for meeting entry.
4. The private chat function will be disabled.
5. The General chat function will be used. Examples of General chat use may include sharing approved resources and PRISM app passwords (as described in Section 9.4), communicating if there are technical difficulties, and the accommodation of specific needs by participant's request (e.g. if a patient has a medical reason that may impact verbal communication).

## 13.0 Provisions to Monitor the Data to Ensure the Safety of Subjects

### 13.1 Data collection

Data collection will occur at each of the 4 enrolling study sites: SCH, BCM, UPMC, and CHLA. Data collection will consist of self-report questionnaires and electronic ECG recordings from HRV monitors. Research material collected will be in the form of data from standardized questionnaires, digital ECG files, and also from medical record information extracted from the patient's electronic medical record. Protected health information (PHI) is accessible only by site PIs and key study personnel.

### 13.2 Data Management

Research material collected will be in the form of data from the standardized questionnaires, digital ECG files and medical record information. Protected health information (PHI) is accessible only by the site PIs and key study personnel, and the on-site monitoring from the coordinating site (SCH). A variety of measures will be utilized to ensure participant privacy. Minimal paper records, such as consent forms, will be kept in a locked drawer in the site PIs' research offices. No identifiable patient information will be labeled on the surveys or ECG

files; all will be identified with a study-specific identifier with assigned identifier kept on a password protected encrypted server. Data will be stored in an electronic database (REDCap -Research Electronic Data Capture) using the participant's study identifier. REDCap data collection projects rely on a thorough study-specific data dictionary defined as an iterative self-documenting process by all members of the research team. We have conducted the iterative development and testing process previously, resulting in well-planned data collection. REDCap servers are housed in a data center and all web-based information transmission is encrypted. REDCap was developed specifically around HIPAA-Security guidelines and is recommended to researchers at various institutions by both Privacy Officers and Institutional Review Boards. REDCap has been disseminated for use locally and at other institutions and currently supports over 300 academic/non-profit consortium partners on six continents and over 20,000 research end-users ([www.project-redcap.org](http://www.project-redcap.org)). The REDCap data record may contain some identifying information. Subjects will be tracked using their study identifier. The identifiable data will be designated as "PHI" in the REDCap database which will allow us to exclude access to the identifiable information as necessary.

### 13.3 Survey Data

The study questionnaire ("Resilience in Pediatric Cancer Assessment", RPCA) and the intervention ("Promoting Resilience in Stress Management", PRISM) may address sensitive matters. Participants may be prompted to think about the threat to their life posed by their cancer/tumor, as well as other difficult topics such as psychological distress, grief, bereavement, and health behaviors. The topics to be covered may provoke sadness, anxiety, depression, fear or doubt.

While surveys will be coded to protect anonymity and do not include instruments to directly measure suicidal ideation or other self-harming behaviors, they will be reviewed within 72 hours by the site study team for (a) missingness (see 13.4.1 below); and (b) unanticipated immediate threats to participants' or others' safety. As part of their informed consent process, participants will be made aware of the survey-review timeline as well as the fact that confidentiality may be broken in the case that providers see an immediate threat to the patient's or another's safety. No physical risks are expected to arise from the study.

If indicated, referral for consultation will include a direct phone call (or in-person consultation) by PI or research team member to recommend further help. This would include alerting: a) current therapist (if they have one), and b) their oncology social worker. The participant will also be given the phone number to the Seattle Children's, Baylor College of Medicine, or Children's Hospital of Los Angeles outpatient psychiatric clinic. County-specific crisis line phone numbers will also be provided as needed.

In the event of other concerns from interventionists and/or other study staff based on interactions with AYAs and families, as well as in other cases of concern for patient or others' safety, the same processes will occur, including immediate referrals to the site PI, and the patients' primary medical and social work teams for in-person evaluation or referral to the appropriate mental health professional if warranted. After hours, the site PI and on-call providers from the medical teams will be notified. All study-related concerns for patient or other person's safety will be reported as an adverse event (AE) to the IRB and Data Safety Monitoring Committee (DSMC, see "Data Safety Monitoring Plan"), within 1 week of study staff awareness. In addition, the PI will review the potential risks and reported findings at least once monthly with study staff from all participating sites. While this is not a pharmacologic

trial and we do not anticipate medical complications, sites will nevertheless notify the IRB and DSMC of all participant deaths at the time of study renewal (annually). Unanticipated (non-medical) participant deaths will be reported to the DSMC within 1 week with a determination if the event might be attributable to the study. In such cases, the DSMC chair may convene the committee and/or suspend the study for additional review (see section 13.5 below).

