### 9.3.2 RCT participants:

**9.3.2.1 Baseline Survey Completion.** Upon enrollment, study staff will deliver the baseline survey in participant's preferred language (English or Spanish). The study will first be offered by email via REDCap or via REDCap on a study team iPad. Upon request, staff will offer paper-pencil versions and/or interview-based versions.

**9.3.2.2 Randomization.** Patients will be randomized following completion of baseline RPCA surveys. Staff will aim for the RPCA surveys to be completed immediately following enrollment. Baseline surveys will be collected within the two weeks. If surveys are not completed within this time-frame, staff will return to the participant to confirm interest and offer a digital (or, when requested paper-pencil or interview-based) survey to be completed. If participants do not complete the survey at that time, they will be removed from the study. For those who do complete the survey, following completion, staff at each site will register participants and receive their randomization allocation. They will then return to patients and families to relay this information and create a study calendar outlining survey due-dates and, where relevant, PRISM sessions. Where relevant, PRISM-sessions will be scheduled approximately every other week, beginning within the first week of enrollment following survey completion.

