All of the sessions of the PRISM will be audio-recorded as possible, barring issues with the recorder or refusal of the patient to be recorded. Sessions will not be recorded through WebEx, Zoom, or Skype platforms. Administrators of PRISM will explain that the sessions will be taped and reviewed by the study team with the goal of assessing adherence to the protocol, inclusion of required elements, and presence/absence of additional information with the exception of the feedback questions. As possible, the PI or supervising team member will review the first 6 sessions for each interventionist, and score them for fidelity using a standardized tool (see appendix). After the first 6 sessions are reviewed for each interventionist, approx. one in every 5 sessions will be randomly selected to be monitored for fidelity, with feedback and re-training regarding adherence to protocol and approach to be refined if needed.

Participants on the intervention arm will also receive once every other week “booster” contacts until they reach the 3 month point from enrollment, for both the run in and the RCT. These will include brief (10-20 minute) in-person contacts in clinic, in the hospital, via phone or other web

based communication (Zoom, WebEx, or Skype) or by email and will consist of opportunities to practice specific skills (at the patient's discretion). Study staff will contact patients to coordinate such visits and will prompt them by asking: "Would you like to review or practice any of the resilience skills?" [If needed, staff will remind patients of all 5 sessions. If patients are willing, study staff will ask,] "Which one?"

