**13.6.4 Identification, review and report of adverse events and unanticipated problem.**

Adverse events information will be collected at all assessment points and recorded on standard forms. We will collect information on all potential types of adverse events. Consistent with NIH and the sites IRBs policies, adverse events will be promptly reported in writing to the NIH, individual IRBs, and the DSMC chair. The DSMC will modify or stop the study if any such complaints represent a legitimate concern about the study procedures or methods.

**13.6.5 Compliance with monitoring requirements.** Compliance with the monitoring plan will be ensured through the Lead RA's close supervision. The Lead RA will hold no less than monthly calls with the sites to monitor recruitment and protocol adherence. Site RAs will gather required information on an ongoing basis and send monthly written reports to Lead RA. The Lead RA will schedule yearly on-site monitoring visits as the coordinating site for data completeness and accuracy. Site RAs will assist in providing on-site monitors with appropriate access to all study related charts and databases during the visit.**13.6.6 Assessment of relevant external factors.** Given the characteristics of the intervention, it is unlikely that a breakthrough result from another study will change the course of this study.**13.6.7 Interim analysis plan.** A primary endpoint interim analysis to assess for safety and missingness will be led by the study statistician after half of the targeted sample size of participants have reached the primary endpoint. The DSMC will determine a priori stopping occurrence of serious events, including (but not limited to) stopping the study for efficacy if interim analysis is significant. For efficacy endpoint, if an effect were found, the DSMC will be presented with unblinded results (i.e. they will be able to ascertain which results correspond to the intervention arm). Based on these results, the DSMC will present recommendations to the study team regarding early stopping or continuation of the trial. There are no pre-planned stopping rules for adverse events since these are not anticipated.**14.0 Withdrawal of Subjects****14.1 Plan for Non-Responders**

Response to the intervention will be determined upon study completion (not in “real-time.”). All participants, including those on the intervention arm, will continue to receive usual care, including as-needed referrals for professional psychology services.

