### **15.0 Risks to Subjects**

The intervention (“Promoting Resilience in Stress Management”, PRISM) and our surveys may address sensitive matters in that it they patients to identify stressors and negative thoughts. Adolescent and young adult participants may be prompted to think about the threat to their life posed by their cancer/tumor. During the coming together session and/or while completing surveys, parents may be prompted to think about the threat to their child’s life by their cancer/tumor. The topics to be covered may provoke sadness, anxiety, depression, fear or doubt for AYAs and/or their parents. Any spouse, caregiver, significant other, caregiver, etc. who participates in the coming together session may be also prompted to think about the threat to the AYA’s life posed by their cancer/tumor and these topics may provoke sadness, anxiety, depression, fear or doubt for AYAs and/or their parents.

Administrators of the intervention will be trained to inform the patient’s primary social work and/or medical teams if the patient and/or parents/guardians/spouses/significant others endorse thoughts of self-harm or harm to others. As part of their informed consent process, participants will be made aware of this policy, as well as the fact that confidentiality may be broken in the case that providers see an immediate threat to the patient’s or another’s safety. Patients who participate in the optional HRV measurement component of the study may experience some mild physical discomfort or skin irritation associated with wearing the ECG monitor. The risk is minimal, as this process is identical to standard ECG measurements obtained for clinical purposes, of which all participants will have undergone. No significant physical risks are expected to arise from the study. The primary risk to participants will be concerns about confidentiality, and stress of discussing the topic of their or their child’s cancer/tumor experience. While the potential risks to participants are low, we will take steps to ensure that all potential risks are handled appropriately as described

below. Due to the nature of the PRISM intervention, all staff and participants will be unblinded from the time of randomization.

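### Concern-triggered adverse events are ascertained more intensively on PRISM than on usual care, and the plan does not record how each event was found

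*Combined protocol and SAP*

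**What the plan says.** Adverse events enter the record in two ways.

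- **Systematic, both arms.** Section 13.6.4: "Adverse events information will be collected at all assessment points and recorded on standard forms".
- **Triggered by a concern.** Section 13.3 covers worries that arise in contact with families ("In the event of other concerns from interventionists and/or other study staff based on interactions with AYAs and families") and then states: "All study-related concerns for patient or other person's safety will be reported as an adverse event (AE) to the IRB and Data Safety Monitoring Committee". In section 15.0 the duty to escalate disclosures of self-harm or harm to others is written for the people who deliver PRISM: "Administrators of the intervention will be trained to inform the patient’s primary social work and/or medical teams".

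Contact before month 3 differs by arm.

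- **PRISM.** Section 9.3.2.2: "PRISM-sessions will be scheduled approximately every other week, beginning within the first week of enrollment following survey completion". Section 9.4 describes five main sessions and the Coming Together session, and adds: "Participants on the intervention arm will also receive once every other week “booster” contacts until they reach the 3 month point from enrollment". It also provides for recording ("All of the sessions of the PRISM will be audio-recorded as possible, barring issues with the recorder or refusal of the patient to be recorded"), with a sample of sessions reviewed for fidelity.
- **Usual care.** Section 9.6 places the RCT surveys up to month 3 at baseline and week 12. It ties the control check-in visit to the abbreviated survey at months 6, 9 and 12.

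Under sections 13.6.3, 13.6.4 and 13.6.7 the Data Safety Monitoring Committee (DSMC) considers adverse events, may ask for unblinded data, and may change or stop the study. An interim analysis at half the target sample is meant to look at safety. There are no pre-planned stopping rules for adverse events. No section says how an event found in a session is to be told apart from one found at a common assessment.

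**The concern.** One reporting route depends on a staff member being present to hear something, and that presence is scheduled mainly in one arm. With identical true risk, more events would then be recorded on PRISM.

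The imbalance falls on the outcome that matters most for safety here. Section 13.6.3 directs monitoring at significant or unexpected distress. Section 13.3 says the surveys do not directly measure suicidal ideation or self-harm, so the shared survey route is weak for those events. Section 15.0 leaves staff and participants unblinded from randomization.

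Without a record of the detection route, an excess on PRISM could be greater detection or real harm from sessions on sensitive topics, and the DSMC could not tell which. It might act on an artefact or dismiss a true signal. The route may be impossible to reconstruct if it is not captured when the event is reported.

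**Working it through.** The plan states no adverse-event rate or power, so there is no figure of its own to reproduce. The check counts contacts and then illustrates the effect.

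**1. Scheduled PRISM contacts, weeks 1 to 12** (sections 9.3.2.2 and 9.4; six sessions, then boosters every two weeks)

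- Sessions every two weeks: weeks 1, 3, 5, 7, 9, 11 = 6 contacts.
- Sessions weekly (section 9.4 gives one to two weeks for the original PRISM): weeks 1 to 6, then boosters at weeks 8, 10, 12 = 6 + 3 = 9 contacts.

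These are scheduled counts. Combining modules, opting out of Coming Together or taking boosters by email would change the number or intensity of contacts.

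**2. Scheduled control contacts over the same period**

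- An allocation visit, which both arms receive (9.3.2.2).
- Survey reminders, also in both arms, possible from about week 12 − 4 = week 8, because the window opens 28 days before the due date (9.6).
- At Seattle only, and only with consent to HRV, a 1-month monitor time point (3.1; Table 6 in 9.7.2).
- Nothing else in the readable text. Figure 3B, the RCT schedule, is not shown. Table 6 labels 1 month a survey time point, which section 9.6 does not list for the RCT; the two need reconciling.

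**3. Routes shared by both arms**

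Adverse-event forms at assessment points (13.6.4), survey review within 72 hours (13.3), and monthly chart abstraction to month 3 (9.5.1). The abstraction covers psychiatric medication, unanticipated hospital days and psychosocial encounters, but lists no adverse-event item.

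**4. Illustration under equal true risk**

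Let *p* be the true risk in each arm, *s* the probability that a shared route detects an event, and *x* the probability that PRISM contacts detect one the shared routes missed. All three are assumptions. The 98 per arm is from 11.3.1.1.

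- Control detection = *s*
- PRISM detection = 1 − (1 − *s*)(1 − *x*)
- Apparent ratio = PRISM detection / *s*, which does not depend on *p*

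With *p* = 10%, there are 9.8 true events per arm:

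| *s* | *x* | PRISM detection | Recorded, PRISM vs control | Ratio | Chance of a nominally significant PRISM excess |
|---|---|---|---|---|---|
| 0.8 | 0.25 | 1 − 0.2 × 0.75 = 0.85 | 8.3 vs 7.8 | 1.06 | 3% |
| 0.5 | 0.50 | 1 − 0.5 × 0.50 = 0.75 | 7.4 vs 4.9 | 1.50 | 11% |
| 0.3 | 0.75 | 1 − 0.7 × 0.25 = 0.825 | 8.1 vs 2.9 | 2.75 | 36% |

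The last column is a normal approximation for a two-sided 5% test and counts only the direction against PRISM, so its no-bias reference is 2.5%. For the bottom row it is 20% at *p* = 5% and 64% at *p* = 20%.

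Restricted to shared routes, detection is *s* in both arms and the expected ratio is 1.00.

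**The case against.** More contact is inherent in comparing a session-based programme with usual care, and several stronger readings that a reader might infer are not supported.

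- **That any distress heard in a session becomes an adverse event.** Section 13.3 limits the reporting duty to study-related concerns about safety.
- **That controls have no contact at all.** They have the allocation visit, possible reminders and, for some, HRV contact. Section 13.3 also covers staff other than interventionists, and Figure 3B cannot be checked.
- **That the ratio is 3 to 5.** Seven chances of detection against one gives this: with 10% per contact, (1 − 0.9^7)/0.1 = 0.52/0.10 = 5.2; with 30%, (1 − 0.7^7)/0.3 = 0.92/0.30 = 3.1. The per-contact rates are not in the documents, contacts are treated as independent, and the control side has only one chance, with no separate allowance for chart abstraction.
- **That a planned by-arm safety comparison is invalid.** None is specified. Questionnaire data go to the DSMC pooled, unblinding is at its option or follows an efficacy finding, and action on adverse events rests on judgement.
- **That an excess on PRISM must be artefact.** Sections 13.3 and 15.0 acknowledge that the sessions may provoke sadness, anxiety or fear.

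The last point also counts against limiting the formal comparison to common assessment points. Before month 3 that leaves baseline, which precedes randomization, and week 12, and session-provoked harm would drop out.

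These objections limit the size and reach of the problem. They do not remove the difference in ascertainment or supply a way to interpret it.

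**Conclusion.** Ascertainment of concern-triggered adverse events is unequal by design: about 6 to 9 scheduled contacts plus sampled recording review on PRISM, against no scheduled check-in for controls between the allocation visit and the week-12 survey process, apart from optional Seattle HRV contact. This holds on the readable text, with Figure 3B unseen.

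The consequence is conditional. It arises if adverse events are tabulated by arm, as in an unblinded DSMC review, the interim safety review or the final report. Pooled counts would then tend to run against PRISM under equal true risk. The documents do not fix the size; about 1.1 to 2.75 follows from assuming *s* between 0.3 and 0.8 and *x* between 0.25 and 0.75. The primary PedsQL analysis is not affected. This is a cheap improvement.

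**What to change.** Add a detection-route field to the adverse-event form with four values: common assessment point or survey review; chart abstraction; PRISM session, booster or recording review; other.

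State in 13.6.4 and 13.6.7 that any by-arm adverse-event summary shows all events and, beside them, events from routes common to both arms. Events detected through sessions, boosters or recordings are also listed separately and stay within the safety review. All events continue to be acted on and reported as now.

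The cost is one form field, a sentence in each of the two sections and one extra table. The common-route comparison will contain few events and will be imprecise, so it should be read with the all-events summary and not in place of it.
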